16.11.2. Hypersensitivity Reactions (HSR)

Drug reaction with eosinophilia and systemic symptoms syndrome (SMQ)

PT	PT Code
Drug reaction with eosinophilia and systemic symptoms	10073508
Pseudolymphoma	10037127
Granulomatous T-cell pseudolymphoma	10084214

PTs (select)

PT	PT Code
Drug hypersensitivity	10013700
Hypersensitivity	10020751
Type IV Hypersensitivity reaction	10053613
Eosinophilia	10014950
Eye swelling	10015967
Eyelid oedema	10015993
Lip swelling	10024570
Angioedema	10002424
Circumoral oedema	10052250
Face oedema	10016029
Idiopathic angioedema	10073257
Lip oedema	10024558
Mouth swelling	10075203
Oedema mouth	10030110
Periorbital oedema	10034545
Swelling face	10042682
Periorbital swelling	10056647
Swelling of eyelid	10042690
Polymers allergy	10086347

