8.2. Adverse Events of Special Interest Analyses

Adverse events of special interest (AESI) are determined for CAB and/or RPV based on pre-clinical and clinical experience, along with information for the Integrase Inhibitor class of HIV medications and RPV safety profile. Table 4 shows the currently identified AESI, drug(s) of Interest and the reasons for inclusion. Changes to the MedDRA dictionary may occur between the start of the study and the time of reporting and/or emerging data from ongoing studies may highlight additional adverse events of special interest, therefore the list of terms to be used for each event of interest and the specific events of interest will be based on the safety review team (SRT) agreements in place at the time of reporting.

A summary by system organ class and preferred term will be provided for each of AESI. The characteristics of event occurrences during the maintenance phase will be summarized for AESIs. For Depression, anxiety and suicidal ideation/behaviour AESI, a summary by system organ class, maximum DAIDS toxicity grade and prior history of suicidal ideation will be provided.

The details of the current planned grouping, including Standardized MedDRA Query (SMQ) values (as applicable), and planned displays are provided in Appendix 11: Identification of Adverse Events of Special Interest (AESI) and Appendix 15: List of Data Displays.

Table 4 Adverse Events of Special Interest

Adverse Events of Special Interest	Drug(s) of Interest	Reason for Inclusion
Hepatic Safety Profile: Assessment of Risk of hepatotoxicity	CAB+RPV	Clinical, Class, Regulatory Interest, More prevalent in HIV population
Hyperglycemia	CAB	Class, Regulatory Interest
Hypersensitivity Reactions (HSR)	CAB	Class, Regulatory Interest, Occurs in HIV population
Rash	RPV	Class, Regulatory Interest, Occurs in HIV population
Prolongation of the Corrected QT Interval of the ECG in Supratherapeutic Doses	RPV	Non-clinical, Clinical, Regulatory Interest
Suicidal Ideation/Behaviour	CAB+RPV	Clinical, Class, Regulatory Interest, More prevalent in HIV population
Depression	CAB+RPV	Clinical, Class, Regulatory Interest, More prevalent in HIV population
Bipolar Disorder	CAB+RPV	Clinical, Class, Regulatory Interest, More prevalent in HIV population
Psychosis	CAB+RPV	Clinical, Class, Regulatory Interest, More prevalent in HIV population
Mood Disorders	CAB+RPV	Clinical, Class, Regulatory Interest
Anxiety	CAB+RPV	Clinical, Class, Regulatory Interest

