16.11. Appendix 11: Identification of Adverse Events of Special Interest (AESI)

The adverse events of special interest are identified based on MedDRA coded values and/or AE data available in the study database. The PT terms and codes below are from MedDRA 24.1. SMQs use narrow terms unless otherwise specified. In case there is a change to the version of MedDRA at time of reporting, the coded values based on the MedDRA version at the time of reporting will be used. Additional events may be added based on the blinded review of AE data collected on study prior to the database freeze.

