3.68.	Safety	SAF_T17	Summary of Substance and Illicit Drug Use (Maintenance Phase)	Q2M vs. BIK	M12
eC-SSRS					
3.69.	Safety	CSSRS1	By Phase Summary of Subjects with eC-SSRS Suicidal Ideation or Behaviour	207966/primary_15/T3.72 Q2M and BIK	M6, M12

Safety: Tables					
No.	Population	GSK Standard/ Example Shell	Title	Programming Notes	Deliverable [Priority]
AEs of Special Interest (AESI)					
3.70.	Safety	207966/primary_15/T3.73	By Phase Summary of Depression, Anxiety and Suicidal Ideation/Behaviour Adverse Events by System Organ Class, Preferred Term, Maximum DAIDS Toxicity Grade, and Prior History (Depression, Anxiety or Suicidal Ideation) at Screening	
3 Layers of section headers:
 
Phase: Oral Lead-In Period(Maintenance)/Maintenance
 
Treatment: Q2M, OLI(Q2M), D2I(Q2M), BIK
 
Subjects has: yes/no prior history of depression, yes/or prior history of anxiety, yes/or prior history of suicidal ideation
 
For Oral Lead-In period, only need to present the OLI(Q2M) groups
	M6, M12, EOS
3.71.	Safety	SAF_T16a and SAF_T16b	By Phase Summary of Adverse Events of Special Interest by AESI Category , System Organ Class and Preferred Term (Number of Subjects and Occurrence)	207966/primary_15/T3.75	M6, M12, EOS
3.72.	Safety	207966/primary_15/T3.109	By Phase Summary of Characteristics of Adverse Events of Special Interest	Add footnote: AESIs with at least 1 event are included in the summary.	M6, M12, EOS
3.73.	Safety	207966/primary_15/T3.111 and T3.112	By Phase Summary of Syncope and Presyncope Adverse Events		M6, M12, EOS
COVID-19 Assessments					
3.74.	Safety	207966 primary 15/Table 3.113	Summary of COVID-19 Adverse Events by System Organ Class, Preferred Term and Maximum Toxicity (Maintenance Phase)	Q2M and BIK only	M6, M12

Safety: Tables					
No.	Population	GSK Standard/ Example Shell	Title	Programming Notes	Deliverable [Priority]
3.75.	Safety	PAN1 / PAN1A	Summary of COVID-19 Assessments for Subjects with COVID-19 Adverse Events	Q2M and BIK only	M6, M12
3.76.	Safety	PAN3 / PAN3A	Summary of COVID-19 Symptoms for Subjects with COVID-19 Adverse Events	Q2M and BIK only	M6, M12
Additional Analysis					

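### The current Hypersensitivity Reactions AESI term list in SAP 16.11.2 contains no anaphylactic, anaphylactoid or Type I hypersensitivity term, so such an event would be missing from that category unless the list is revised before reporting

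*SAP*

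**What the plan says.** Table 4 in SAP section 8.2 makes hypersensitivity an AESI for cabotegravir: "Hypersensitivity Reactions (HSR) CAB Class, Regulatory Interest, Occurs in HIV population". The same section commits to a display for every category: "A summary by system organ class and preferred term will be provided for each of AESI". Appendix 15 carries this out in Table 3.71, "By Phase Summary of Adverse Events of Special Interest by AESI Category", which goes down to system organ class and preferred term, and in Table 3.72, which gives the characteristics of the events. Both are planned for Month 6, Month 12 and End of Study.

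Section 16.11.2 sets out which coded terms count as HSR. It has two blocks:

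- one standardised query, "Drug reaction with eosinophilia and systemic symptoms syndrome (SMQ";
- a block of selected preferred terms, with entries such as "Drug hypersensitivity 10013700" and "Angioedema 10002424", ending with "Polymers allergy 10086347".

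The introduction to Appendix 11 sets the scope of the queries: "SMQs use narrow terms unless otherwise specified". It also allows events to be added after a blinded look at the AE data before database freeze. Section 8.2 says that the terms finally used will follow the safety review team's agreements at the time of reporting.

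**The concern.** A category called Hypersensitivity Reactions should collect the recognised forms of hypersensitivity. The list covers drug reaction with eosinophilia and systemic symptoms (DRESS), general hypersensitivity terms, a Type IV reaction, eosinophilia and many forms of facial swelling. Anaphylactic and anaphylactoid reactions are absent, and the Type IV term has no Type I counterpart. The SAP gives no reason.

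What is at stake is the grouping of a safety event. Under the list as written, one report of eye swelling enters the HSR rows and an event coded as an anaphylactic reaction does not. Table 3.72 includes only AESIs with at least one event. If the only hypersensitivity event in the trial were coded to an absent term, HSR would therefore not appear in that table at all. Someone relying on the AESI tables for the hypersensitivity profile would have to know to look elsewhere.

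**Working it through.** The plan gives no figure to reproduce. The check is a count of the list and a reading of the other places that could catch the event.

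**1. Count of section 16.11.2.**

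| Block | Entries |
|---|---|
| DRESS query | 3 |
| Drug hypersensitivity; Hypersensitivity; Type IV reaction; Eosinophilia | 4 |
| Angioedema, oedema and swelling terms | 14 |
| Polymers allergy | 1 |

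Selected terms: 4 + 14 + 1 = 19. All entries: 3 + 19 = 22. A text search of the 22 for anaphylaxis or shock terms returns none, and reading them shows no Type I term.

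**2. Other Appendix 11 categories.** No term list in 16.11.1 to 16.11.17 contains an anaphylactic, anaphylactoid or Type I term. Two nearby categories do not fill the gap:

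- Rash (16.11.3) consists of severe cutaneous reactions and rash terms.
- Injection site reactions (16.11.12) takes the non-serious injection-site form and those serious events whose reported term names the study drug injection site.

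The pregnancy category (16.11.18) has no term list and covers only events reported with a pregnancy exposure.

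**3. Other hypersensitivity displays.** Listings 57 to 63 in section 16.15.12 concern abacavir hypersensitivity only.

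**4. Where the event would still be seen.** By preferred term it would be in:

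- Tables 3.4 and 3.5 (all AEs, and by maximum toxicity);
- Tables 3.13 and 3.20, if serious;
- Table 3.17, if it led to withdrawal or permanent discontinuation.

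Listing 12 covers all AEs, Listings 14 to 17 fatal and non-fatal serious events and withdrawals, and Listing 38 Grade 3 to 5 events.

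**5. Scale.** Section 2.3 plans about 654 participants randomised 2:1.

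- Q2M: 654 × 2/3 = 436, so one participant is 1/436 = 0.23%.
- BIK: 654 × 1/3 = 218, so one participant is 1/218 = 0.46%.

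These are planned sizes; the Safety population may differ slightly. The SAP gives no expected rate for such events in either arm, so no expected number can be calculated.

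**The case against.** The strongest reply is that the list is not final. Section 8.2 treats Appendix 11 as the current plan and ties the terms used to the safety review team's agreements at reporting. The introduction to Appendix 11 lets events be added after blinded review. This stands in part: the omission can be put right without breaching the plan, so it cannot be said outright that such an event will go uncounted. But neither provision names these terms, and addition after data review is optional. In an open-label trial, adding a foreseeable term once a case has appeared is weaker than naming it beforehand.

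A second reply is that the selection is deliberate, since the block is headed as selected terms, and that nothing in the SAP promises to capture anaphylaxis. It is true that no passage contradicts another here. But no reason for the exclusion is given, and Appendix 11 is not evidently complete: Hyperglycemia is in Table 4 and has no term list.

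A third reply is that the event stays visible by preferred term, and that for a rare event individual listings tell more than a grouped count. This stands, and it limits the point to the AESI grouping.

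Three stronger readings are tempting but unsupported:

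- **That one case would move the category from no serious reaction to one.** This assumes no other serious HSR event. DRESS, drug hypersensitivity and angioedema are all on the list and could be serious.
- **That the profile is understated for the injectable arm in particular.** The same list applies to both arms, and the SAP gives no rate by arm.
- **That the most serious hypersensitivity reaction is the one left out.** The SAP does not rank these reactions, and DRESS is included.

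**Conclusion.** The point holds as a minor gap in a pre-specified safety grouping. As written, 16.11.2 and the rest of Appendix 11 have no anaphylactic, anaphylactoid or Type I hypersensitivity term. An event coded to one, in either arm, would be left out of the HSR category in Tables 3.71 and 3.72.

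This rests on two assumptions. The first is that the safety review team's list at reporting does not add the terms. The second is that the event is coded to its own preferred term and not to one already listed, such as Hypersensitivity or Angioedema; in the latter case it would be counted.

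If it occurs, the effect is on a descriptive count, by one participant at a time. The event is not lost to safety reporting, and no hypothesis test, estimate or efficacy conclusion depends on it.

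**What to change.** In section 16.11.2, pre-specify the anaphylactic and anaphylactoid reaction terms and the Type I counterpart of the listed Type IV term. Confirm the exact query and preferred-term names against the MedDRA version used at reporting, because they cannot be verified from the SAP. If the sponsor means to leave them out, state the reason there. No extra table line is needed: Table 3.71 already reports by preferred term within category.

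The cost is a few lines of SAP text and a slightly longer list applied to AE data that are already coded. The HSR count may rise a little, and the list may differ slightly from any list used across the development programme. Because Tables 3.71 and 3.72 are also Month 6 deliverables, a note should say from which analysis the longer list applies.

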16.11.3. Rash**Severe cutaneous adverse reactions (SMQ)**

PT	PT Code
Acute generalised exanthematous pustulosis	10048799
Bullous haemorrhagic dermatosis	10083809
Cutaneous vasculitis	10011686
Dermatitis bullous	10012441
Dermatitis exfoliative	10012455
Dermatitis exfoliative generalised	10012456
Drug reaction with eosinophilia and systemic symptoms	10073508
Epidermal necrosis	10059284
Erythema multiforme	10015218
Erythrodermic atopic dermatitis	10082985
Exfoliative rash	10064579
Oculomucocutaneous syndrome	10030081
SJS-TEN overlap	10083164
Skin necrosis	10040893
Stevens-Johnson syndrome	10042033
Target skin lesion	10081998
Toxic epidermal necrolysis	10044223
Toxic skin eruption	10057970
Generalised bullous fixed drug eruption	10084905
Severe cutaneous adverse reaction	10085778

PTs (Select)

PT	PT Code
Eyelid rash	10074620
Genital rash	10018175
Mucocutaneous rash	10056671
Nodular rash	10075807
Perineal rash	10075364
Rash	10037844
Rash erythematous	10037855
Rash generalised	10037858
Rash macular	10037867
Rash maculo-papular	10037868
Rash maculovesicular	10050004
Rash morbilliform	10037870

PT	PT Code
Rash papular	10037876
Rash rubelliform	10057984
Rash scarlatiniform	10037890
Rash vesicular	10037898
Rash pruritic	10037884
Rash follicular	10037857
Rash pustular	10037888
Drug eruption	10013687

16.11.4. Prolongation of the Corrected QT Interval of the ECG in Supratherapeutic Doses

Torsade de pointes/QT prolongation (SMQ)

PT	PT Code
Electrocardiogram QT interval abnormal	10063748
Electrocardiogram QT prolonged	10014387
Long QT syndrome	10024803
Long QT syndrome congenital	10057926
Torsade de pointes	10044066
Ventricular tachycardia	10047302

PTs (Selective)

PT	PT Code
Electrocardiogram repolarisation abnormality	10052464

16.11.5. Suicidal Ideation/Behaviour

Suicide/self-injury (SMQ)

PT	PT Code
Assisted suicide	10079105
Columbia suicide severity rating scale abnormal	10075616
Completed suicide	10010144
Depression suicidal	10012397
Intentional overdose	10022523
Intentional self-injury	10022524
Poisoning deliberate	10036000
Self-injurious ideation	10051154

PT	PT Code
Suicidal behaviour	10065604
Suicidal ideation	10042458
Suicide attempt	10042464
Suicide threat	10077417
Suspected suicide	10082458
Suspected suicide attempt	10081704

16.11.6. Depression

Depression (excl suicide and self injury) (SMQ)

PT	PT Code
Activation syndrome	10066817
Adjustment disorder with depressed mood	10001297
Adjustment disorder with mixed anxiety and depressed mood	10001299
Agitated depression	10001496
Anhedonia	10002511
Antidepressant therapy	10054976
Childhood depression	10068631
Decreased interest	10011971
Depressed mood	10012374
Depression	10012378
Depression postoperative	10012390
Depression rating scale score increased	10084390
Depressive symptom	10054089
Discouragement	10084257
Dysphoria	10013954
Electroconvulsive therapy	10014404
Feeling guilty	10049708
Feeling of despair	10016344
Feelings of worthlessness	10016374
Helplessness	10077169
Major depression	10057840
Menopausal depression	10067371
Mixed anxiety and depressive disorder	10080836
Perinatal depression	10078366
Persistent depressive disorder	10077804
Post stroke depression	10070606
Postictal depression	10071324

16.11.7. Bipolar Disorder**HLGT Manic and Bipolar mood disorders and disturbances**

PT	PT Code
Bipolar I disorder	10004939
Bipolar II disorder	10004940
Bipolar disorder	10057667
Cyclothymic disorder	10011724
Hypomania	10021030
Mania	10026749
Manic symptom	10084119

16.11.8. Psychosis**Psychosis and psychotic disorders (SMQ)**

PT	PT Code
Acute psychosis	10001022
Alcoholic psychosis	10001632
Alice in wonderland syndrome	10001666
Brief psychotic disorder with marked stressors	10048549
Brief psychotic disorder without marked stressors	10056395
Brief psychotic disorder, with postpartum onset	10006362
Charles Bonnet syndrome	10063354
Childhood psychosis	10061040
Clang associations	10009232
Cotard's syndrome	10059591
Delusion	10012239
Delusion of grandeur	10012241
Delusion of parasitosis	10012242
Delusion of reference	10012244
Delusion of replacement	10012245
Delusion of theft	10084030
Delusional disorder, erotomanic type	10012249
Delusional disorder, grandiose type	10012250
Delusional disorder, jealous type	10012251
Delusional disorder, mixed type	10012252
Delusional disorder, persecutory type	10053195
Delusional disorder, somatic type	10012254
Delusional disorder, unspecified type	10012255

PT	PT Code
Delusional perception	10012258
Dementia of the Alzheimer's type, with delusions	10012295
Depressive delusion	10063033
Derailment	10012411
Epileptic psychosis	10059232
Erotomanic delusion	10015134
Flight of ideas	10016777
Hallucination	10019063
Hallucination, auditory	10019070
Hallucination, gustatory	10019071
Hallucination, olfactory	10019072
Hallucination, synaesthetic	10062824
Hallucination, tactile	10019074
Hallucination, visual	10019075
Hallucinations, mixed	10019079
Hypnagogic hallucination	10020927
Hypnopompic hallucination	10020928
Hysterical psychosis	10062645
Ideas of reference	10021212
Illusion	10021403
Jealous delusion	10023164
Loose associations	10024825
Mixed delusion	10076429
Neologism	10028916
Neuroleptic-induced deficit syndrome	10075295
Paranoia	10033864
Paranoid personality disorder	10033869
Parkinson's disease psychosis	10074835
Paroxysmal perceptual alteration	10063117
Persecutory delusion	10034702
Postictal psychosis	10070669
Post-injection delirium sedation syndrome	10072851
Posturing	10036437
Psychosis postoperative	10065617
Psychotic behaviour	10037249
Psychotic disorder	10061920
Psychotic disorder due to a general medical condition	10061921
Reactive psychosis	10053632
Rebound psychosis	10074833

PT	PT Code
Schizoaffective disorder	10039621
Schizoaffective disorder bipolar type	10068889
Schizoaffective disorder depressive type	10068890
Schizophrenia	10039626
Schizophreniform disorder	10039647
Schizotypal personality disorder	10039651
Senile psychosis	10039987
Shared psychotic disorder	10040535
Somatic delusion	10041317
Somatic hallucination	10062684
Substance-induced psychotic disorder	10072388
Tangentiality	10043114
Thought blocking	10043495
Thought broadcasting	10052214
Thought insertion	10043496
Thought withdrawal	10043497
Transient psychosis	10056326
Waxy flexibility	10047853
Negative symptoms in schizophrenia	10084992
Pseudohallucination	10066297

16.11.9. Mood Disorders

HLGT Mood disorders and disturbances

PT	PT Code
Affect lability	10054196
Affective ambivalence	10077173
Affective disorder	10001443
Alexithymia	10077719
Anger	10002368
Apathy	10002942
Blunted affect	10005885
Boredom	10048909
Constricted affect	10010778
Crying	10011469
Diencephalic syndrome of infancy	10012774
Discouragement	10084257
Dysphoria	10013954
Emotional disorder	10014551

PT	PT Code
Emotional distress	10049119
Emotional poverty	10014557
Euphoric mood	10015535
Flat affect	10016759
Frustration tolerance decreased	10077753
Inappropriate affect	10021588
Irritability	10022998
Laziness	10051602
Lethargy	10024264
Listless	10024642
Moaning	10027783
Mood altered	10027940
Mood disorder due to a general medical condition	10027944
Mood swings	10027951
Morose	10027977
Neuroleptic-induced deficit syndrome	10075295
Premenstrual dysphoric disorder	10051537
Premenstrual syndrome	10036618
Screaming	10039740
Seasonal affective disorder	10039775
Steroid withdrawal syndrome	10042028
Substance-induced mood disorder	10072387
Sibling rivalry disorder	10086385

16.11.10. Anxiety

HLGT Anxiety disorders and symptoms

PT	PT Code
Acrophobia	10000605
Activation syndrome	10066817
Acute stress disorder	10001084
Aerophobia	10080300
Agitation	10001497
Agitation postoperative	10049989
Agoraphobia	10001502
Akathisia	10001540
Algophobia	10078056
Animal phobia	10002518
Anniversary reaction	10074066

PT	PT Code
Anticipatory anxiety	10002758
Anxiety	10002855
Anxiety disorder	10057666
Anxiety disorder due to a general medical condition	10002859
Arachnophobia	10051408
Astraphobia	10078372
Autophobia	10071070
Body dysmorphic disorder	10052793
Burnout syndrome	10065369
Catastrophic reaction	10082329
Cibophobia	10082413
Claustrophobia	10009244
Compulsions	10010219
Compulsive cheek biting	10076510
Compulsive handwashing	10071263
Compulsive hoarding	10068007
Compulsive lip biting	10066241
Compulsive shopping	10067948
Cryophobia	10082662
Dermatillomania	10065701
Dysmorphophobia	10049096
Emetophobia	10070637
Fear	10016275
Fear of animals	10016276
Fear of closed spaces	10016277
Fear of crowded places	10050365
Fear of death	10066392
Fear of disease	10016278
Fear of eating	10050366
Fear of falling	10048744
Fear of injection	10073753
Fear of open spaces	10016279
Fear of pregnancy	10067035
Fear of surgery	10084519
Fear of weight gain	10016280
Fear-related avoidance of activities	10080136
Generalised anxiety disorder	10018075
Glossophobia	10080077
Haemophobia	10073458

PT	PT Code
Haphephobia	10067580
Herpetophobia	10081809
Hydrophobia	10053317
Hyperarousal	10080831
Immunisation anxiety related reaction	10075205
Kinesiophobia	10078430
Limited symptom panic attack	10024511
Mysophobia	10078769
Nail picking	10066779
Nervousness	10029216
Neurosis	10029333
Noctiphobia	10057946
Nocturnal fear	10057948
Nosocomophobia	10083993
Nosophobia	10063546
Obsessive need for symmetry	10077179
Obsessive rumination	10056264
Obsessive thoughts	10029897
Obsessive-compulsive disorder	10029898
Obsessive-compulsive symptom	10077894
Ochlophobia	10050095
Osmophobia	10060765
Paediatric autoimmune neuropsychiatric disorders associated with streptococcal infection	10072147
Panic attack	10033664
Panic disorder	10033666
Panic reaction	10033670
Paruresis	10069024
Performance fear	10034432
Phagophobia	10050096
Pharmacophobia	10069423
Phobia	10034912
Phobia of driving	10056676
Phobia of exams	10034913
Phobic avoidance	10034918
Phonophobia	10054956
Photopiophobia	10064420
Postpartum anxiety	10082233
Postpartum neurosis	10036419
Postpartum stress disorder	10056394

PT	PT Code
Post-traumatic stress disorder	10036316
Procedural anxiety	10075204
Pseudoangina	10056610
Selective mutism	10039917
Separation anxiety disorder	10040045
Sitophobia	10080170
Social anxiety disorder	10041242
Social fear	10041247
Stress	10042209
Tension	10043268
Terminal agitation	10077416
Thanatophobia	10064723
Thermophobia	10075147
Trichotemnomania	10072752
Trichotillomania	10044629
Aichmophobia	10085292
Olfactory reference syndrome	10085053
Frigophobia	10086104
Somniphobia	10085856

